(4) Long-Term Outcome: This pilot is not powered to detect change in suicide death rates (the outcome most likely affected by lethal means safety). We will assess suicidal behavior at phone follow-up (self-report of SI/SA) using the "since last visit" C-SSRS,⁹¹ as well as via structured review of electronic medical records (ED visits for SI/SA) and vital statistics (deaths) at 1 and 3 months.

(5) Trial Feasibility Outcomes:

- **Eligibility and participation rates:** We will record demographic information (gender, age group, race/ethnicity) and reasons for non-eligibility or non-participation for patients not enrolled in this pilot trial to inform our planned trial. We will also record participant disposition (discharge home versus hospitalization) and how often participants have a family member or friend present in the ED (with willingness of companion to participate). We will analyze these data for each of the clinical sites.
- **Follow-up rates:** We will record rates for telephone follow-up at 1-week.
- **Suicide composite measure:** We will record the feasibility of accessing medical records and vital statistics.
- **Provider training:** Measures will include estimated training time required for competence (an important feasibility measure for future implementation) as well as user feedback about the training itself.

Analysis: We will describe the three sites in terms of demographics as well as the primary measure (DCS score <25) using appropriate statistical tests (e.g. anova, chi-square). If no differences are found between the three sites, we will ignore site and compare the proportion of the primary measure in the control and intervention groups as the primary analysis. If differences are found among sites and there are enough events, we will use a logistic regression model with a fixed effect for site and with a treatment indicator as the main predictor. Missing data for the primary measure should be minimal, given that this will be obtained before patients leave the ED. For secondary measures, we will use descriptive statistics including proportions with 95% confidence intervals for knowledge, acceptability and feasibility; whether the criteria in Table 1 have been met will be based on the confidence intervals of the proportions.

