ED Providers (n=100)	
 • Physicians, physician extenders (i.e., physician assistants or nurse practitioners), nurses, and behavioral health evaluators (e.g., social workers, psychologists, advanced practice nurses) who work in the participating EDs • Cared for ≥ 1 participating patient • Completed current care of participating patient(s) prior to beginning the survey 	
 • Current or former member of the study team (i.e. PI, CO-I, RA)

C. Study Design and Research Methods: In this pilot randomized controlled trial, we will test the LM-DA in a sample of 60 adult patients being evaluated for suicide risk at three large hospital EDs. Thirty nine patients will be randomized to the LM-DA group, while 21 will be randomized to the control group (13/7 at each site). Figure 2 displays the overall study flow. Analysis and reporting will follow CONSORT guidelines, and we will register the trial on clinicaltrials.gov. Family member or friends who are concurrently enrolled will also be enrolled in the ED, in the same randomization group as the patient. ED Providers will be surveyed separately.

Study Sites: To prepare for the subsequent multi-site trial, including by identification of moderators of LM-DA and study feasibility at different sites, the pilot will recruit patients, family members/friends, and providers from the EDs at three large, diverse Colorado Hospitals: (1) University of Colorado Hospital (tertiary care center without dedicated psychiatric ED; suburban Denver; part of UCHealth consortium); (2) Memorial Hospital

(hospital with dedicated psychiatric ED; draws from large catchment area in southern Colorado, including rural and urban populations; high firearm ownership rate; part of UCHealth consortium); and (3) Denver Health Medical Center.

Figure 2. General Study Flow

Enrollment:

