- ED Providers: Provider survey invitations will be emailed and will include a unique link to complete a REDCap online survey. To supplement these survey data, we will conduct qualitative interviews with 20 ED providers to further explore LM-DA acceptability, feasibility of real-world implementation, and training. All providers who are a part of a patient –subject’s clinical team will be invited by email to participate in the initial survey. At the end of the survey, there will be an invitation to participate in a follow-up qualitative interview. Interested providers will be instructed to email or call the study team, as their name will not be on the survey. If more providers opt for qualitative surveys than anticipated, we will select a sample to optimize balance across provider groups and sites.
- All participants will receive a gift card as an incentive (\$25 for patients; \$10 for family or friends; \$5 for providers who complete the online survey; \$15 for providers who complete a qualitative interview for a total incentive of \$20).

Randomization:

- Patients: At each ED, enrolled patients will be randomly assigned to the LM-DA or control arm (Figure 2). To reduce bias and achieve balance among arms, we will randomize patients in blocks.⁹⁰
- Family members/friends: If a family member or friend is concurrently enrolled, they will be automatically randomized into the same arm as the patient, as they will potentially be reviewing the LM-DA with the patient and assisting with decision making.
- ED Providers: Providers will be asked to provide answers to a survey after the patient’s visit. Thus, they are not randomized, nor can they feasibly be blinded given their ongoing care relationship with patients during the study.

Baseline Measurements & Intervention:

- Patients: The RA will give the patient a study tablet with an introductory short survey and basic information about suicide prevention. In the intervention arm only, patients will then complete the LM-DA on the tablet. All patients in both arms will answer questions about their ED care and their anticipated care plan (including knowledge about the rationale for reducing access to firearms as a safety measure, and their intent to decrease access to firearms at home). Study participation will not affect clinical care, including discharge or admission planning.

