
Another area of challenge is blinding to treatment arm. RAs will carry out all study procedures

Figure 3. Time Spent in ED by a Patient with SI/SA

but cannot feasibly be blinded to study arm, as they will need to ensure the patient can access the LM-DA. To blind patients, we plan to use deception (with IRB approval) in the informed consent process such that patients know

the study is examining ways to enhance safety of suicidal patients but do not know that the LM-DA is the intervention of interest. ED providers will not be blinded to participant study group, as providers may review the LM-DA printed results with patients (as they would in real-world implementation). We will notify providers of the study at the start of enrollment and explain the purpose, with the request that providers continue to provide usual care (with or without LMC, as per their usual practice) for patients in the intervention and control groups. A third challenge is testing the role of family or friends. Not all suicidal patients have someone present with them in the ED, so there will be real-world variability in how family or friends are involved with DA completion. Ideally, the person with decision-making control over firearm storage would be involved, but may not be present with the patient. In the current proposal, we will record how often family or friends are present and are (or are not) the ones with control of firearm storage. We will also record how often they are willing to participate in the study – all of these findings will help lay the groundwork for future study. If we find any aspects of the LM-DA are unacceptable, we will revise those aspects and re-review with stakeholders prior to future implementation. Another limitation is finding differences across sites, but not enough events to adjust for site (with a fixed effect). In this case, given that this is a pilot study, we will use two strategies: (1) ignore site and summarize the overall results, and (2) analyze the results ignoring the site with few events. A future study will allow to account for differences across sites.

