F. Data Analysis Plan: We will describe the three sites in terms of patient demographics as well as the primary measure (DCS score <25) using appropriate statistical tests (e.g. anova, chi-square). If no differences are found between the three sites, we will ignore site and compare the proportion of the primary measure in the control and intervention groups as the primary analysis. If differences are found among sites and there are enough events, we will use a logistic regression model with a fixed effect for site and with a treatment indicator as the main predictor. Missing data for the primary measure should be minimal, given that this will be obtained before patients leave the ED. For secondary measures, we will use descriptive statistics including proportions with 95% confidence intervals for knowledge, acceptability and feasibility; whether the criteria in Table 1 have been met will be based on the confidence intervals of the proportions. Keeping in mind factors related to pilot trial feasibility, our target sample size (n=60; 30 LM-DA and 30 control) was chosen to allow detection of a 30% difference between the LM-DA and control arms for the primary measure (DCS score <25; Table 2) While this sample size will not allow for full power to analyze moderators by site (as related to either LM decision or trial feasibility measures), it should generate adequate pilot information concerning site selection for the subsequent trial. Participants and RAs will enter survey data directly into REDCap. Participants completing REDCap surveys will be sent a unique link for participation. For follow-up calls, chart reviews and other documents, RAs will enter data into REDCap or store it on password-protected university servers. We will export data to SAS for analyses.

G. Summarize Knowledge to be Gained: The proposed research will provide the scientific foundation for improvement and examination of real-word implementation of an effective, patient-centered LM-DA in EDs and other settings. A web-based tool offers the potential to significantly enhance current care, decrease real-world access to lethal means of suicide, and thereby decrease short-term risk of suicide.

H. References:

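### Site enters the primary analysis only after a check that uses the primary outcome, and the few-events fallback gives two unranked results, one omitting a whole site

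*Combined protocol and SAP*

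**What the plan says.** Site is part of the design. Under Randomization in section IV.C, "At each ED, enrolled patients will be randomly assigned to the LM-DA or control arm", in blocks. Section IV.C also gives the split: "Thirty nine patients will be randomized to the LM-DA group, while 21 will be randomized to the control group (13/7 at each site").

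The analysis treats site as optional. Section IV.F begins: "We will describe the three sites in terms of patient demographics as well as the primary measure (DCS score <25) using appropriate statistical tests". Three branches follow.

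1. **No site differences:** "If no differences are found between the three sites, we will ignore site and compare the proportion of the primary measure" between the arms.
2. **Differences, enough events:** "If differences are found among sites and there are enough events, we will use a logistic regression model with a fixed effect for site" and a treatment indicator. The Analysis paragraph of section IV.A uses the same wording.
3. **Differences, too few events:** covered only in section IV.E, which starts "Another limitation is finding differences across sites, but not enough events to adjust for site (with a fixed effect") and goes on: "we will use two strategies: (1) ignore site and summarize the overall results, and (2) analyze the results ignoring the site with few events".

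The plan does not give a significance level for the site check, say whether a demographic difference alone opens branches 2 and 3, say how many events are enough, or say which branch 3 result is primary.

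**The concern.** The outcome data choose the model. In branch 3 they also choose which randomised patients count, because the site left out is identified by its number of outcome events. Defining enough events would not cure this, since the check uses the primary outcome under any threshold.

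Two things are at stake. First, branch 3 has no single headline result: one estimate describes 60 patients and the other 40. Second, neither analysis uses all the information. Ignoring site leaves between-site variation in the error term, and dropping a site discards a third of the sample. An analysis stratified by site uses both site and all 60 patients, and the randomisation already supports it.

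**Working it through.** **The plan's own figure.** The sample-size table (80% power, alpha 0.05) reproduces with the usual two-proportion formula, two-sided, 1:1, without continuity correction:

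n per arm = [1.960·√(2p̄(1−p̄)) + 0.842·√(p₀(1−p₀)+p₁(1−p₁))]² / (p₁−p₀)²

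For 0.30 v 0.65, p̄ = 0.475: (1.384 + 0.557)² / 0.1225 = 30.75, so 31 per arm and 62 in total, as printed. The rows for 0.50 v 0.85 (54) and 0.20 v 0.55 (58) also match. Control rates of 0.3 and 0.2 are inferred from the differences because the table is broken. The calculation takes no account of site and uses all patients.

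**Losing one site.** This leaves 26/14 of 39/21. Exact power of the chi-square test, whatever the route to the exclusion:

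| Control v decision aid | 39/21 | 26/14 |
|---|---|---|
| 0.50 v 0.85 | 83.4% | 66.3% |
| 0.30 v 0.65 | 75.2% | 60.5% |
| 0.20 v 0.55 | 77.4% | 63.1% |

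**Simulating the rule.** 400,000 trials per scenario.

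- From the plan: 13/7 per site, and the 0.30 v 0.65 row, giving odds ratio (0.65/0.35)/(0.30/0.70) = 4.33.
- Assumed: the site control rates; a 3×2 chi-square site check at 0.05; few meaning under 3 or under 5 events at a site; the lowest-event site is dropped.
- Stratified test: Cochran-Mantel-Haenszel (CMH), Σ(aᵢ − 13mᵢ/20) squared, divided by Σ 13·7·mᵢ(20−mᵢ)/(20²·19), where aᵢ is decision-aid events and mᵢ all events at site i. It also stands in for the plan's site-adjusted logistic model.

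Results within branch 3, each pair reading under 3 / under 5:

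| Control rates | Branch reached (%) | Power, site ignored (%) | Power, site dropped (%) | Power, CMH, all patients (%) | Two results disagree on significance (%) |
|---|---|---|---|---|---|
| 0.1/0.3/0.6 | 9 / 42 | 39.5 / 47.3 | 51.4 / 51.0 | 57.5 / 61.0 | 11.9 / 13.7 |
| 0.15/0.3/0.45 | 1 / 13 | 49.6 / 57.1 | 58.4 / 57.6 | 61.7 / 65.4 | 8.8 / 14.2 |
| 0.05/0.3/0.5 | 46 / 86 | 43.9 / 48.9 | 55.9 / 55.8 | 59.7 / 61.9 | 12.0 / 12.7 |

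At 0.1/0.3/0.6 the mean estimated difference in this branch is 23 or 26 points ignoring site and 31 with the site dropped (true value 28). The two differ by at least 10 points in 31% or 22% of these trials.

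Across all trials, with either branch 3 result as headline:

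| Control rates | Plan's rule | CMH always |
|---|---|---|
| 0.05/0.3/0.5 | 52–61% | 63% |
| 0.1/0.3/0.6 | 59–64% | 65% |
| 0.15/0.3/0.45 | 70–71% | 71% |
| 0.2/0.3/0.5 | 71.5–71.9% | 72.2% |
| 0.2/0.5/0.5 | 70.1–70.6% | 70.9% |

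**Other inputs.** With 10/10 per site (sections IV.A and IV.F give 30/30) at 0.1/0.3/0.6, branch 3 is reached in 16% or 57% of trials, and the rule's power is 60.3–67.3% against 69.0%. With an odds ratio of 3.5, about the 30-point effect named in section IV.F, the figures are 15% or 55%, and 44.2–50.5% against 51.5%. A demographic trigger moves the figures at odds ratio 4.33 by about 1 point at most.

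**No treatment effect.** Branch 3 is then more common: 67% or 89% at 0.1/0.3/0.6, but 3% or 5% with equal rates of 0.3. If either result may be claimed, type I error is 4.9–5.5%, or up to 6.4% if a demographic difference always opens the branch. Counting few non-events as well gave 4.1–6.1%.

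**The case against.** The strongest case is about weight. The scenarios with a visible loss all have a site control rate of 0.15 or less, while the lowest control rate in the planning table is about 0.2. At 0.2/0.3/0.5 with the planned effect, branch 3 is reached in only 0.2% or 3.6% of trials, and the overall power loss is under 1 point. That stands.

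The stratified estimate is also no different in value. At exactly 13/7 the Mantel-Haenszel weight is 13·7/20 = 4.55 at every site, so the weighted risk difference equals the crude one. The low mean of 23 or 26 points comes from conditioning on reaching the branch, and stratifying does not remove it. The gain is in the standard error and the test. That stands too.

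A leave-one-site-out analysis also compares 60 patients with 40. The fault is therefore not that a site-excluded result is shown, but that it has no subordinate status and that outcomes choose which site goes.

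Finally, this is a pilot, section IV.E discloses the limitation, its first strategy may be purely descriptive, and no Table 1 threshold is stated as a test of this comparison. These points lower the stakes. They do not say which result is primary, and if the first strategy is only descriptive, the sole analysis left in that branch excludes a site. The plan does name a primary comparison and size the trial for it.

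**Conclusion.** The point holds, with low to moderate weight: it should be changed, but it does not threaten the trial. That branch 3 has no designated primary result, and that one of its analyses omits a site selected on outcome, follows from the text under any assumption.

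The power cost depends on assumed site rates, an assumed 0.05 site check and an assumed meaning of few. Within branch 3, CMH on all patients beats the better of the two planned analyses by about 3 to 10 points in the scenarios tabulated. Over all trials the loss runs from under 1 point, when control rates are all 0.2 or higher, to about 11 points (52% against 63%) at 0.05/0.3/0.5 in the least favourable reading. It is not a false-positive problem, and where events are judged sufficient the site check costs almost nothing (64.8% against 64.9% at 0.1/0.3/0.6, with CMH in place of the logistic model).

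**What to change.** In sections IV.A and IV.F, name one primary analysis that depends on no site test or event count: a CMH test stratified by site, without continuity correction, in all randomised patients at all three sites. Report one estimate with it, the Mantel-Haenszel-weighted risk difference with its site-stratified Miettinen-Nurminen score 95% interval. At zero difference that score statistic equals the CMH statistic, so test and interval cannot conflict. In simulation the interval's coverage was 94.8–95.6%. Keep site comparisons descriptive. In section IV.E, replace the low-event exclusion with a leave-one-site-out analysis run for every site and labelled as sensitivity.

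A lighter change, naming the all-site result primary and the exclusion a sensitivity analysis, would end the ambiguity but not recover the power.

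The cost is wording, plus about 0.2 points of power if sites are alike (74.9% against 75.1%). A site with no events, or only events, adds nothing to the stratified test. That happens in 0.7% of trials at 0.1/0.3/0.6 and 4.9% at 0.05/0.3/0.5, or 12% and 36% if the decision aid has no effect. No event threshold is needed: the type I error of CMH within branch 3 was 4.9–5.8%. The change should be made before outcome data are seen.

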Sample Size: Keeping in mind factors related to pilot trial feasibility, our target sample size ($n=60$; 30 LM-DA and 30 control) was chosen to allow detection of a 35% difference between the LM-DA and control arms for the primary measure (DCS score <25 ; Table 2). In a prior small study, 62% of parents of at-risk youth who received LMC reduced home

Table 5. Sample Size Estimates			
Control	LM-DA	% with DCS <25	Total Detectable sample size
		0.6	64
0.5	0.8	0.3	78
	0.85	0.35	54
	0.9	0.4	40
	0.6	0.3	84
	0.65	0.35	62
	0.7	0.4	48
0.3	0.5	0.3	78
	0.55	0.35	58
80% power, $\alpha=0.05$			

access to firearms, compared to 0% of those who did not receive LMC.⁴⁹ Estimates for the effect of LMC on behavior among adults with suicide risk do not exist, so our assumption of a 35% difference is conservative (prior work with other DAs has found an effect size of 40-80% on DCS between groups⁹²). While this sample size will not allow for full power to analyze moderators by site (as related to either LM decision or trial feasibility measures), it should generate adequate pilot information concerning site selection for the subsequent trial.

B. Description of Population to be Enrolled: We will enroll three populations:

- a. 60 patients seen in the ED for SI/SA
- b. Up to 60 influential adult family members or friends (one per enrolled patient), either in person or by telephone (if not present in the ED; n=60 total). Enrollment of a family member or friend will not be required for a patient to participate.
- c. 100 emergency department providers for surveys and 20 for qualitative interviews (may participate in survey, interview or both)

Table 3. Inclusion/Exclusion Criteria

[figure not shown]
	Inclusion	Exclusion
Patients (n=60)	
 • Being evaluated in the emergency department for SI/SA. • Deemed medically stable by ED physician • Age ≥ 18 years • Able and willing to have telephone follow up at 1 week • Report ≥ 1 firearm at home 	
 • Unable to participate medically or cognitively (e.g. sustained altered level of consciousness, hostility, psychosis, sexual assault victim, severe vomiting or pain) • Currently in legal custody • Live in group home or other supervised custody • Already enrolled
Family member or friend (n=60)	
 • Age ≥ 18 years 	
 • Unable to participate cognitively • Already enrolled • Currently in legal custody

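### The Data Analysis Plan says 60 patients detect a 30-point difference; the Sample Size section says 35, and the protocol's own table supports 35

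*Combined protocol and SAP*

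**What the plan says.** The combined protocol and SAP justifies the sample size twice, in almost the same sentence.

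- Sample Size (within section IV.A): n=60, 30 per arm, "was chosen to allow detection of a 35% difference between the LM-DA and control arms for the primary measure". The rationale that follows repeats the figure: "so our assumption of a 35% difference is conservative".
- Section F, Data Analysis Plan: "our target sample size (n=60; 30 LM-DA and 30 control) was chosen to allow detection of a 30% difference".

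Both sentences name the proportion with DCS below 25 as the endpoint, and both cite Table 2. The only sample size table is headed Table 5. It is set at 80% power and alpha 0.05 and does not state sidedness.

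Section C (Study Design and Research Methods) gives a different allocation: "Thirty nine patients will be randomized to the LM-DA group, while 21 will be randomized to the control group".

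No allowance is made for missing primary data: "Missing data for the primary measure should be minimal, given that this will be obtained before patients leave the ED".

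**The concern.** Both statements are current text, and both figures stand in running prose, so damage to the table cannot explain the difference. With the same total, split, endpoint, power and alpha, 60 patients cannot have been sized for both 30 and 35 points.

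The smaller figure is the more favourable one, and it sits in the analysis section, where a reader goes to interpret the result. Someone relying on it would take a null result as stronger evidence against a 30-point effect than 60 patients can give. The pilot is meant to inform a larger trial, so its sensitivity should be stated correctly.

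**Working it through.** **Inputs.** Total 60, 30 per arm (Sample Size; section F). Power 80% and alpha 0.05 (Table 5). Differences 0.30 (section F) and 0.35 (Sample Size). Alternative allocation 39/21 (section C). Sidedness is taken as two-sided because that reproduces the table.

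Control rates come from Table 5, which is damaged in the text available. Only 0.5 is printed beside a row that it fits. The rates 0.3 and 0.2 are obtained by subtracting the difference from the LM-DA rate. The rate 0.6 is inferred from an incomplete row with total 64.

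**Step 1: reproduce the table.** Pooled-variance normal approximation, equal arms, no continuity correction, with p̄ = (p1 + p2)/2:

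n per arm = [1.960·√(2p̄(1−p̄)) + 0.842·√(p1(1−p1) + p2(1−p2))]² / (p2−p1)²

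For 0.3 vs 0.6: p̄ = 0.45, and [1.960·√0.495 + 0.842·√0.45]² / 0.09 = 41.97. Rounded up this is 42 per arm, 84 in total.

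| Control vs LM-DA | Difference | Table 5 total | Recomputed total |
|---|---|---|---|
| 0.5 vs 0.8 | 0.30 | 78 | 78 |
| 0.3 vs 0.6 | 0.30 | 84 | 84 |
| 0.2 vs 0.5 | 0.30 | 78 | 78 |
| 0.5 vs 0.85 | 0.35 | 54 | 54 |
| 0.3 vs 0.65 | 0.35 | 62 | 62 |
| 0.2 vs 0.55 | 0.35 | 58 | 58 |
| 0.5 vs 0.9 | 0.40 | 40 | 40 |
| 0.3 vs 0.7 | 0.40 | 48 | 48 |

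All eight readable rows match. The incomplete row with total 64 fits 0.6 vs 0.9; 0.1 vs 0.4 also gives 64. Either way it exceeds 60. So n=60 lies among the 0.35 totals (54 to 62) and below every total for 0.30.

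**Step 2: power with 60 patients.**

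Power = Φ[(d − 1.960·SE0)/SE1], where d is the difference, SE0 = √(p̄(1−p̄)(1/n1+1/n2)) with p̄ weighted by arm size, and SE1 = √(p1(1−p1)/n1 + p2(1−p2)/n2).

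For 0.3 vs 0.6 at 30/30: SE0 = √(0.45·0.55·2/30) = 0.1285 and SE1 = √(0.45/30) = 0.1225. Then (0.30 − 0.2518)/0.1225 = 0.394, and Φ(0.394) = 65%.

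| Control rate | 30/30: power, 30 points | 30/30: power, 35 points | 30/30: detectable at 80% | 39/21: power, 30 points | 39/21: power, 35 points | 39/21: detectable at 80% |
|---|---|---|---|---|---|---|
| 0.2 | 69% | 82% | 34.3 | 63% | 77% | 36.2 |
| 0.3 | 65% | 79% | 35.4 | 61% | 75% | 37.0 |
| 0.5 | 69% | 84% | 33.4 | 67% | 82% | 34.2 |
| 0.6 | 78% | 92% | 30.6 | 77% | 91% | 31.0 |

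Detectable differences are in percentage points, solved numerically.

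**Step 3: exact check.** Enumerating all outcomes for the uncorrected chi-square test with a 30-point difference, at control rates 0.2, 0.3, 0.5 and 0.6, gives power of 69.2%, 66.3%, 69.2% and 79.6% at 30/30, and 64.0%, 61.2%, 67.6% and 78.7% at 39/21. The normal approximation is close enough for this purpose.

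**The case against.** The strongest reply is that this is a slip in one number, in a pilot whose main aims are acceptability and feasibility. The dedicated Sample Size section gives 35% twice, with a rationale and beside the table, so the intended basis for n=60 can be recovered. No threshold in Table 1 depends on the 30% figure. All of that stands, and it limits the severity. It does not make the sentence in section F correct.

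The size of the shortfall also depends on the control rate. At 0.6, exact power for 30 points at 30/30 is 79.6%, essentially nominal, so the lower end of the shortfall is negligible. That rate is inferred from an incomplete row, and 0.2 and 0.3 rest on subtraction. The difference and total columns are readable without those inferences, however, and they are enough to show 78, 84 and 78 against 60.

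A one-sided test at 0.05 would bring 30 points close: totals of 62 to 66 at control rates 0.2 to 0.5. These still exceed 60, and one-sided values do not reproduce the table.

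Section F names no power level of its own. The 80% comes from the table, which is taken to be the one cited as Table 2 because it is the only sample size table.

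Finally, the 30/30 versus 39/21 conflict is a separate inconsistency, and the 30 versus 35 contradiction does not depend on it. It matters here only because it decides which detectable difference is the correct one to print.

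**Conclusion.** The concern holds. Section F claims a detectable difference that 60 patients do not provide at the power and alpha of the protocol's own table, and it contradicts the Sample Size section.

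At 30/30, a true 30-point effect would be missed about 22% to 35% of the time by the normal approximation (22% at control 0.6, 35% at control 0.3), or about 20% to 34% by exact enumeration, against the nominal 20%. The gap is material at control rates of about 0.2 to 0.5 and small at 0.6. By contrast, 35 points is supported at 30/30, with power of 79% to 92%.

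This rests on a two-sided test at 0.05, no loss of primary data, and the control rates reconstructed from Table 5. The consequence is moderate: the stated sensitivity is wrong, but no decision rule in the plan uses it. It should be corrected.

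**What to change.** Put one identical sentence in the Sample Size section and section F, with a single detectable difference, the assumed control rate, power, alpha and sidedness. Compute it for the allocation actually used, after reconciling the 30/30 statements with the 39/21 statement in section C. Over control rates of 0.2 to 0.6 the figure is about 31 to 35 points at 30/30, or about 31 to 37 points at 39/21.

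Alternatively, keep 30 points and state the power that 60 patients give for it: about 65% to 78% at 30/30, or about 61% to 77% at 39/21.

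Correct the table reference at the same time (cited as Table 2, printed as Table 5).

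The cost is one sentence in two places and a less favourable detectable difference, or power, in section F. Enrolment, endpoint and test do not change.
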